USE OF AUTOMATIC PERIODIC
STIMULATION AND
CONTINUOUS EMG FOR FACIAL
NERVE MONITORING DURING
PAROTIDECTOMY

NCT03172520

November 21, 2016

USE OF AUTOMATIC PERIODIC STIMULATION AND CONTINUOUS EMG FOR FACIAL NERVE MONITORING DURING PAROTIDECTOMY

Principal Investigators:

[name] and [name]

Version 2
November 21, 2016

TABLE OF CONTENTS

	Page
STUDY SUMMARY	3
1. INTRODUCTION	4
2. BACKGROUND	4
3. STUDY OBJECTIVES	5
4. STUDY DESIGN	5
4.1 General Design	5
4.2 Primary Study Endpoints	6
4.3 Secondary Study Endpoints	6
4.4 Early termination.....	6
5. SUBJECT ENROLLMENT AND WITHDRAWAL	6
5.1 Inclusion Criteria	6
5.2 Exclusion Criteria	6
5.3 Subject Recruitment	7
5.4 Withdrawal of Subjects	7
6. STUDY PROCEDURES	7
6.1 Preoperative Visit	7
6.2 Operative Visit	7
6.2.1 Intraoperative Facial Nerve Monitoring	8
6.2.2 Facial Nerve Monitoring Malfunction	8
6.3 Postoperative Visit #1	8

7. DATA COLLECTION AND ANALYSIS	9
7.1 Data to be Collected	9
8. DATA HANDLING	10
9. STUDY FUNDING	10
10. REFERENCES	11
APPENDIX A (ELECTRODE PLACEMENT)	12
APPENDIX B (APS ELECTRODE PACAKGE INSERT).....	13

STUDY SUMMARY

Title: Use of Automatic Periodic Stimulation and Continuous EMG for Facial Nerve Monitoring During Parotidectomy

IRB Protocol Number: 16-009380

Methodology: Prospective, investigational

Target subject accrual: 50

Expected duration of study: 6-9 months

Subject participation duration: 2 days (day of surgery and post operative day 1)

Primary Objective: Use of an automatic periodic stimulation electrode to correlate EMG changes during parotidectomy with post-operative facial nerve weakness.

Secondary Objective: Modification of intraoperative technique to decrease the incidence and/or severity of post-operative facial nerve weakness following parotidectomy.

Principal Investigator: [name]

Head Study Coordinator: [name]

1 INTRODUCTION

This is a protocol to direct a prospective, investigational study which aims to evaluate the utility of a facial nerve monitor during parotidectomy in predicting intra-operative factors that portend post-operative facial nerve weakness. Intra-operative facial nerve monitoring has become the “standard of care” at most tertiary care centers but the current method of monitoring the facial nerve and predicting post-operative weakness has several limitations. In the trial, we aim to determine intra-operative factors that are associated with EMG changes on the facial nerve monitor in an effort to alter intra-operative techniques to decrease the incidence and severity of post-operative weakness.

2 BACKGROUND

Parotidectomy is a relatively common procedure for the practicing Otolaryngologist, especially at tertiary care facilities, where most of these procedures are performed. The most dreaded, yet relatively common, complication following parotidectomy is post-operative facial nerve weakness which results in functional, cosmetic, emotional, and financial burden on the patient as well as psychological burden on the surgeon. Transient post-operative facial nerve weakness, occurring in at least one major distribution of the facial nerve, occurs in approximately 20-40% of cases following parotidectomy. Permanent paralysis occurs in approximately 1-5% of cases.

The current method of facial nerve monitoring during parotidectomy was introduced during the late 1980’s and its safety, application, effectiveness, and benefits have been described and documented (Metson et al, 1988, Terrell et al, 1997, Lopez et al, 2001). Current monitoring involves placing transcutaneous electrodes on the patient’s face during general anesthesia in 2-4 muscles innervated by separate branches of the facial nerve. An electrophysiologic monitoring system, for example the NIM-Response 2.0 Nerve Integrity Monitor (NIM-2; Medtronic Xomed, Jacksonville, FL), then monitor facial muscle activity during parotidectomy and alert the surgeon to EMG changes using an integrated pulse generator for electrically- evoked EMG changes. This system has several benefits including identification of the nerve, differentiation between neural and non-neural tissue, alertness of potentially traumatic manipulation, and awareness of nerve proximity when it is not expected. A recent meta-analysis published in 2014 concluded that facial nerve monitoring is safe and effective, resulting in a statistically significant reduction in post-operative facial nerve weakness (Sood et al, 2014).

There are several limitations to the current method of facial nerve monitoring during parotidectomy. EMG changes using standard techniques of facial nerve monitoring are not reliably predictive of impending facial nerve damage and do not allow the surgeon to alter his or her technique to prevent adverse EMG events. Often times, the alert generated by the monitoring system is that of artifact, a change in the depth of the patient’s anesthesia, or occurs after the damage is already done. In addition, the current technique does not allow for “real-time” identification of impending damage and requires the surgeon to use a handheld nerve

stimulator to active the nerve. This requires the surgeon to halt the operation and apply direct contact to the nerve with a handheld device. Changes in the nerve's neural integrity which may predict impending damage can not be detected until the surgeon stimulates the nerve either incidentally or with the handheld stimulator, after which permanent damage may have already occurred. Lastly, current techniques only reflect damage that occurs distal to the point of stimulation, and is not capable of monitoring the nerve's integrity along its entire course.

The use of an automatic-periodic-stimulating (APS) electrode has been proposed, designed, and implemented in thyroid surgery with success and safety. The use of an APS electrode allows for continuous monitoring of a motor nerve during surgery and provides the surgeon with real-time information regarding the integrity of the nerve and maneuvers which are associated with adverse EMG changes. The combination of changes in amplitude and latency (which is not provided by the current method) provide the surgeon with more accurate information regarding EMG changes that are associated with impending nerve damage. More importantly, this information allows the surgeon to alter techniques, in real-time, to avoid damage to the nerve being monitored. This method has been documented as safe and effective in thyroid surgery in monitoring the recurrent laryngeal nerve and preventing temporary vocal fold dysfunction following thyroidectomy (Dionigi et al 2013, Schneider et al 2013, Randolph et al 2014)

3 STUDY OBJECTIVES

Primary Objective: To determine if continuous intraoperative facial nerve monitoring during parotidectomy using an APS electrode is safe, feasible, and informative. We aim to determine if continuous facial nerve monitoring can identify intra-operative EMG changes that are associated with post-operative facial nerve weakness

Secondary Objective: To determine if the information garnered by intra-operative continuous facial nerve monitoring can arm the surgeon with information that may alter the surgical technique and prevent temporary post-operative facial nerve weakness.

4 STUDY DESIGN

4.1 General Design

This study will be conducted in three phases. The first will be that of a pilot study to document safety of this electrode during parotidectomy. This electrode has been used safely in other areas of head and neck surgery and has FDA approval for peripheral nerves throughout the human body. This phase will include 10-15 patients during which the electrode will be placed and either removed or inactivated to ensure that placement of the electrode itself is safe.

The second phase of the trial will aim to accrue approximately 25 patients who will undergo continuous intraoperative facial nerve monitoring with the Medtronic APS electrode. This is the same monitoring system, using the same receiving electrodes that is currently used during

parotidectomy and requires placement of the APS electrode as the only additional piece of equipment. During this phase, we will record intraoperative EMG data generated by the monitoring system as well as document intra-operative maneuvers that precede adverse EMG events. We hope to correlate both EMG changes as well as intra-operative techniques that predict facial nerve damage and post-operative paresis. During this phase, the surgeon will be blinded to the information provided by the APS electrode but will still have the monitoring system functioning in the current standard fashion, alerting the surgeon to stimulated EMG events.

The third phase of the trial will then aim to allow the surgeon to alter his or her techniques, with the information provided by the APS electrode, to reverse adverse EMG changes. The incidence of adverse EMG changes and their relationship to intra-operative maneuvers will be recorded in an effort to identify specific factors during surgery that cause post-operative facial nerve weakness. With this information, we aim to eliminate or minimize those factors so that the incidence of post-operative facial nerve weakness decreases.

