4.2 Primary Study Endpoints

The primary study endpoints include adverse EMG changes, including amplitude and latency, and the degree of post-operative facial nerve weakness as recorded with the APS electrode and standard neural monitoring system.

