4.4 Early termination

If during the pilot study or during the main trial the placement or use of the APS electrode is documented or suspected by the surgeon to cause nerve damage or add unnecessary time or difficulty to the surgery, the study protocol will be revisited and re-written or the study will be terminated.

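### Phase one (10-15 patients, no comparator) can screen only for gross harm from electrode placement, not ensure safety, and failed placements leave the data behind the safety and feasibility claims

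*Protocol*

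**What the plan says.** Section 3 sets out to show that monitoring "using an APS electrode is safe, feasible, and informative". Section 4.1 introduces phase one in these words: "The first will be that of a pilot study to document safety of this electrode during parotidectomy". Its size and exposure follow: "This phase will include 10-15 patients during which the electrode will be placed", after which it is taken out or switched off, so that "the electrode will be placed and either removed or inactivated to ensure that placement of the electrode itself is safe" can be the result. No comparison group is described.

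Section 4.2 opens its endpoint list with "The primary study endpoints include adverse EMG changes, including amplitude and latency" and adds the degree of facial weakness after surgery. Section 6.3 has each patient graded on the Facial Nerve Grading Scale 2.0 (FNGS 2.0) the next morning. Neither section designates that grade as the safety outcome.

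Section 4.4 calls for revision or termination if placement or use of the electrode "is documented or suspected by the surgeon to cause nerve damage or add unnecessary time or difficulty to the surgery". Section 2 says that transient weakness in at least one major distribution "occurs in approximately 20-40% of cases following parotidectomy".

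Section 5.2 lists failure to place the electrode, and a change of surgical technique because of it, among the exclusion criteria. Section 6.2 withdraws any patient who meets an exclusion criterion during the operation.

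**The concern.** The protocol promises that safety of placement will be established before continuous stimulation begins in phase two. The harm at issue is facial weakness, which is common after this operation without the electrode. A small uncontrolled group will therefore contain weak patients whether or not the electrode does harm, and the question is how large an excess such a group could reveal.

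The second problem is who gets counted. A patient in whom the electrode cannot be placed is a feasibility failure. A patient in whom it changes the surgery is also one, and may matter for safety. If both are withdrawn, the remaining patients are selected for uneventful placement, and a conclusion that the method is safe and feasible would be favourable partly by construction.

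**Working it through.** **Inputs from the protocol.** Phase one n = 10 to 15, single group (Section 4.1). Background weakness p0 = 20% to 40% (Section 2), with 30% added as a midpoint. The protocol states no test, error rate or acceptable excess for phase one, so there is no stated figure to reproduce.

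**Assumptions.** One-sided exact binomial test at 5%; excesses of 10 to 40 percentage points shown as a range.

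**Step 1. Expected number weak with a harmless electrode** (n × p0):
- n = 10: 10 × 0.20 = 2 to 10 × 0.40 = 4.
- n = 15: 15 × 0.20 = 3 to 15 × 0.40 = 6.

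The chance of at least one weak patient is 1 − (1 − p0)^n. This runs from 1 − 0.8^10 = 89% to 1 − 0.6^15 = 99.95%.

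**Step 2. What a background-like result leaves open** (Clopper-Pearson 95% intervals):

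| Observed weak | Exact 95% CI |
|---|---|
| 2/10 | 2.5-55.6% |
| 3/10 | 6.7-65.2% |
| 3/15 | 4.3-48.1% |
| 4/15 | 7.8-55.1% |
| 6/15 | 16.3-67.7% |

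Every upper limit lies above the 40% top of the background range, so a moderate rise is not excluded by any of these results.

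**Step 3. What excess would be seen.** The cut-off r is the smallest count with P(X ≥ r | n, p0) ≤ 0.05. Power is P(X ≥ r | n, p0 + excess).

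| n | p0 | r | Actual alpha | +10 | +20 | +30 | +40 |
|---|---|---|---|---|---|---|---|
| 10 | 20% | 5 | 3.3% | 15% | 37% | 62% | 83% |
| 10 | 30% | 6 | 4.7% | 17% | 38% | 63% | 85% |
| 10 | 40% | 8 | 1.2% | 5% | 17% | 38% | 68% |
| 15 | 20% | 7 | 1.8% | 13% | 39% | 70% | 91% |
| 15 | 30% | 9 | 1.5% | 10% | 30% | 61% | 87% |
| 15 | 40% | 10 | 3.4% | 15% | 40% | 72% | 94% |

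Power for a 20-point excess is 17-40%, and for a 40-point excess 68-94%. A doubling from 20% to 40% would be missed about six times in ten (power 37% at n = 10, 39% at n = 15).

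**Step 4. Sensitivity to the discrete cut-off.** Some low values reflect a conservative alpha. At n = 10 and p0 = 40%, lowering r to 7 gives alpha 5.5% and power 38% for 20 points. At n = 15 and p0 = 30%, lowering r to 8 gives alpha 5.00% (fractionally above the limit) and power 50%. Neither approaches adequate power.

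**Step 5. Who is counted.** Section 3 wants a conclusion on safety and feasibility. Section 5.2 makes two forms of electrode failure exclusion criteria, and Section 6.2 applies those criteria during surgery. Read together, patients with either failure leave the study before the day-1 grade is used.

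**The case against.** The strongest reply is that phase one is called a pilot, that Section 4.1 cites safe use elsewhere in head and neck surgery and regulatory approval, and that the power figures judge a test the protocol never proposes. Much of this stands. The test and the excesses are assumptions, and a screen for gross harm is worth having. But Section 4.1 still sets up a phase to establish safety in parotidectomy, and the intervals in Step 2 need no test to show that it cannot do so.

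Several stronger readings are tempting, and the document does not support them:

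- **That there is no safety endpoint.** The degree of weakness is a primary endpoint (Section 4.2) and is graded in each patient (Section 6.3). What is missing is its designation for the safety question. A numerical threshold could properly sit in a statistical analysis plan that is not shown.
- **That phase one can show nothing about harm.** A very large excess would probably be seen (Step 3).
- **That the Section 4.4 rule fires on almost any weak patient.** It needs documented or suspected causation by the electrode, or unnecessary time or difficulty, and may lead only to a rewrite. The 89-99.95% in Step 1 is not its firing probability.
- **That no single case could be attributed to placement.** The electrode sits at the main trunk (Section 6.2.1), while the background figure counts weakness in any one major distribution. Four regions are graded, so the pattern may be informative.
- **That pooling all 50 patients would provide the missing test.** The background range is itself 20 points wide. At n = 50, a test against 20% rejects at 16 or more weak patients. If the true harmless rate is 40%, it rejects 90% of the time. A test against 40% rejects at 27 or more, and flags a real rise from 20% to 40% only 3% of the time. Pooling also mixes placement alone, active stimulation and altered technique.

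**Conclusion.** The concern holds in limited form. With 10-15 uncontrolled patients and a 20-40% background, phase one can reveal gross harm, an excess of about 40 points, but cannot exclude a moderate one. The stated purpose of ensuring safe placement therefore exceeds what the design can deliver. Separately, the withdrawal rules take the feasibility failures, and possibly some safety-relevant patients, out of the data on which the primary objective depends.

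The sizes rest on the Section 2 range applying to this population. It is a general parotidectomy figure, and the Section 5.2 exclusions could shift it. The power figures also rest on the assumed one-sided 5% test. This should be corrected, because it changes what the trial may conclude at almost no cost.

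**What to change.** 1. **Section 4.1:** keep the size of phase one, but describe it as an initial check for gross harm instead of saying that it ensures safe placement.
2. **Section 4.2:** designate day-1 FNGS 2.0 weakness as the safety outcome, and placement success and added operative time as feasibility outcomes, all counted in every patient in whom placement is attempted.
3. **Sections 5.2 and 6.2:** reconcile them with this, so that patients with failed placement or electrode-altered technique stay in the safety and feasibility set even if they leave the EMG correlation analysis.
4. **Reporting:** give the weakness rate with an exact confidence interval for each phase, beside the 20-40% range and without claiming a test against it. Any pooled figure is descriptive only. Limit the conclusion that the method is safe to what those intervals exclude.
5. **Section 4.4:** state that the running day-1 count is looked at beside the stated background when the judgement is made. Any level that prompts review is for the sponsor to set.

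**Cost:** a weaker safety claim after phase one, one extra table and the rewording of these sections. No patients or visits are added: the day-1 visit already exists, and patients with failed placement would simply be kept in the count.

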4.2 Primary Study Endpoints

The primary study endpoints include adverse EMG changes, including amplitude and latency, and the degree of post-operative facial nerve weakness as recorded with the APS electrode and standard neural monitoring system.

4.3 Secondary Study Endpoints

The secondary study endpoints include adverse EMG changes as they relate to intra-operative techniques and maneuvers that their association with post-operative facial nerve weakness.

4.4 Early termination

If during the pilot study or during the main trial the placement or use of the APS electrode is documented or suspected by the surgeon to cause nerve damage or add unnecessary time or difficulty to the surgery, the study protocol will be revisited and re-written or the study will be terminated.

5 SUBJECT ENROLLMENT AND WITHDRAWAL

5.1 Inclusion Criteria

- Age: 18 years of age or older
- Parotidectomy: Planned parotid gland surgery (superficial or total parotidectomy)
- Benign or malignant disease

5.2 Exclusion Criteria

- Age: less than 18 years of age
- Current pregnancy
- Preoperative facial nerve dysfunction
- Revision surgery
- History of preoperative radiation to the surgical field

- Retrograde or extracapsular dissection
- Intentional nerve sacrifice (ie. due to nerve involvement by tumor)
- Tumors with proximity to main trunk of facial nerve
- Inability to place electrode
- Presence of electrode alters surgical technique

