6.2 Operative Visit

Patients enrolled in the study will proceed to the operating room according to the medical decision making between the patient and their surgeon. As a prerequisite for inclusion in the study, the planned operation will be a superficial or total parotidectomy with facial nerve preservation. The surgeon will complete whatever operation is needed for each specific patient, irrespective of their inclusion in the study. If the patient requires a less significant dissection for treatment (ie., partial parotidectomy without facial nerve dissection), or a more significant

dissection (ie., facial nerve sacrifice), then the surgeon will proceed accordingly. The facial nerve monitor will be used intraoperatively. The patient's operative experience will not deviate from standard operating room procedure in any way by their participation in this study, aside from the use of the APS electrode. If during the course of the patient's operation, any of the exclusion criteria are met, the patient will be withdrawn from the study, and will be notified of this on the first postoperative day visit.

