6.2.1 Intraoperative Facial Nerve Monitoring

At the time of surgery, the facial nerve monitor (NIM-Response[®] 3.0; Medtronic, Jacksonville, FL) will be used, as is typical for parotid gland surgery. Four monitoring leads will be used, one in each of the following muscles: frontalis (frontal eminence), orbicularis oculi (lateral orbital rim), levator labii superioris (nasolabial fold), and depressor anguli oris (oral metnalis). Two grounding leads will be placed in the subcutaneous tissue of the patient's chest or shoulder per the standard fashion. The operative team will confirm accurate placement of leads and correct function of the system prior to making a surgical incision. When the main trunk of the facial nerve is identified, the APS electrode will be placed by the primary surgeon (see Appendix A) when it is deemed safe.

The facial nerve monitoring system records the number of stimulations of the facial nerve during the operation and this data is stored on the device until it is shut down after the surgery is complete. With the APS electrode, the monitoring system will be able to record changes in amplitude in isolation or in combination with changes in latency. A 50% decrease in nerve amplitude combined with a 10% increase in nerve latency will be defined initially as an "adverse" EMG event as this combination has been identified in previous studies as predictive of post-operative nerve dysfunction. During the first phase of the trial, the surgeon will be blinded to these changes as the monitoring system will not be prompted to alarm. The surgeon, however, will still have the same feedback that is offered during the standard method of monitoring facial nerve function, which is an alarm generated by a stimulated amplitude generated, the threshold for which is selected by the surgeon.

During the last phase of the trial, the surgeon will be alerted to adverse EMG changes and will be allowed to alter the maneuver in an attempt to reverse or prevent further adverse EMG changes.

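### The undefined trunk-proximity exclusion can be applied after the APS electrode is recording, which permits removal after exposure, with APS alerts visible to the surgeon only in the last phase

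*Protocol*

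**What the plan says.** Among the exclusions in Protocol section 5.2 is "Tumors with proximity to main trunk of facial nerve". The entry gives no distance, basis in imaging, assessor or time of assessment.

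Section 6.2 keeps the whole list in force during surgery: "If during the course of the patient's operation, any of the exclusion criteria are met, the patient will be withdrawn from the study". It adds that the patient "will be notified of this on the first postoperative day visit". Section 6.3 uses the visit on the morning after surgery to grade facial function.

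Section 6.2.1 fixes the moment of exposure: "When the main trunk of the facial nerve is identified, the APS electrode will be placed by the primary surgeon", once that is judged safe.

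The surgeon's knowledge differs by phase. For phase two, section 4.1 says that "the surgeon will be blinded to the information provided by the APS electrode", although the standard stimulated-EMG alarms still sound. For the later stage, section 6.2.1 says: "During the last phase of the trial, the surgeon will be alerted to adverse EMG changes".

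**The concern.** Eligibility should normally be settled before exposure, or at least without knowledge of what exposure reveals. Here a judgement criterion stays open while the monitor is recording. Closeness of the tumor to the trunk plausibly raises the chance of both an adverse EMG change and weakness, so removing such patients late is selection on something related to predictor and outcome.

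The larger worry is the step from phase two to phase three. Section 4.1 hopes that the incidence of weakness will fall once the surgeon can act on APS information. The protocol names no formal comparison, but phase two is the natural reference. If the same loose criterion is judged without APS information in one phase and with APS alerts in the other, the two groups may be filtered differently, and part of any difference in weakness could come from the filter.

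The smaller worry is the phase-two association between EMG change and weakness, which would rest on a narrower population than the one that was monitored.

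**Working it through.** **Order of events.** Setting sections 5.2, 6.2, 6.2.1 and 6.3 side by side gives:

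1. screening and consent;
2. incision and exposure of the trunk;
3. APS placement and recording;
4. the rest of the dissection;
5. end of surgery;
6. day-1 grade.

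The withdrawal rule in 6.2 covers steps 2 to 5. Only step 2 precedes exposure. Nothing requires the proximity decision to fall there, or to be made without sight of EMG.

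**Knowledge at the decision.** In phase two the surgeon has standard alarms only. In the last phase the surgeon also has APS alerts. (Section 6.2.1 attaches the blinding to the first phase. I follow section 4.1, where monitored recording begins in phase two.)

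**Inputs.** Total accrual is 50 (Study Summary). Phase one has 10-15 patients and phase two about 25 (section 4.1). Transient weakness occurs in 20-40% (section 2). No phase-three number is given, so I take it by subtraction: 50 - 25 - 15 = 10, and 50 - 25 - 10 = 15.

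**Loss of k weak patients out of n, with e weak at the start:** rate = (e - k)/(n - k).

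| Starting rate | n | e | k = 1 | k = 2 |
|---|---|---|---|---|
| 20% | 10 | 2 | 1/9 = 11.1% | 0/8 = 0% |
| 20% | 15 | 3 | 2/14 = 14.3% | 1/13 = 7.7% |
| 40% | 10 | 4 | 3/9 = 33.3% | 2/8 = 25.0% |
| 40% | 15 | 6 | 5/14 = 35.7% | 4/13 = 30.8% |

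**The same calculation with other removals.** Removing one weak and four non-weak patients from 3/15 leaves 2/10 = 20%, which is no change. Removing one non-weak patient from 2/10 gives 2/9 = 22.2%, a shift the other way. The shift depends on who is removed.

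**Selection on location alone, with no effect of monitoring.** Let a share f of patients lie near the trunk, with relative risk RR of weakness, and let them be removed in phase three only. The observed rate is p/(1 - f + f × RR). Both f and RR are assumptions; the documents give neither.

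- f = 10%, RR = 1.5: 1/1.05 = 0.952, an apparent relative fall of 4.8%.
- f = 20%, RR = 2: 1/1.2 = 0.833, a fall of 16.7% (40% to 33.3%, or 20% to 16.7%).
- f = 30%, RR = 3: 1/1.6 = 0.625, a fall of 37.5%.

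**The case against.** The strongest reply is that the window is narrow in practice. The electrode goes on the trunk only once the trunk has been found, so a tumor close to it will usually be evident before any APS baseline exists. Patients are also screened at consultation. This stands, and it limits the likely number of late withdrawals. It does not close the window, because no text requires the decision at that point.

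Second, a reader might infer that patients with both an EMG event and weakness are the ones who will be withdrawn, so that the primary association is biased outright. The documents do not support this. Section 6.2 has the criterion met during the operation, and weakness is graded the next morning. Only the notification of withdrawal falls on day 1. In phase two the surgeon cannot respond to APS changes that are not shown. Removal on tumor location there mainly narrows the population.

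Third, the figures build in the answer by assuming that the removed patient is weak, or that removal happens in phase three only. This stands too, so they are illustrations and not estimates.

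Fourth, it is tempting to treat intentional nerve sacrifice as the same problem. It is not. Sacrifice is an observable act that causes weakness by design, and section 6.2 confines the study to planned operations that preserve the nerve. Keeping such patients out of the main EMG-weakness analysis is right.

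Last, analysis sets are often left to a SAP, which is not shown. But eligibility and withdrawal are set in this protocol, and an analysis plan cannot recover a log or grade that was never kept.

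**Conclusion.** The point holds as a fault in a stated rule. Sections 5.2 and 6.2 together allow removal after exposure on an undefined judgement, made with APS alerts visible in the last phase but not in phase two. This could bias a comparison of weakness between those phases. Its effect on the phase-two association is smaller and is mainly one of narrowing.

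The size is unknown. With 10 to 15 patients and 2 to 6 weak in phase three, a single withdrawal of a weak patient is visible in the rate: from 20% to 11.1% or 14.3%, and from 40% to 33.3% or 35.7%. This rests on the phase-three number obtained by subtraction, on the background rate in section 2, and on the withdrawn patient being weak. Proportionate withdrawal changes nothing.

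A reader might conclude that phase three will look safer, or that surgeons will use the criterion to shed difficult cases. The documents show neither. They show only that the rule would allow it and that no record would reveal it.

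**What to change.** - **Section 5.2:** require the proximity decision to be made and recorded before the APS electrode is placed, at the latest when the main trunk is exposed.
- **Section 6.2:** state that after placement no patient is withdrawn from the study data for proximity. Keep the EMG log, where one was recorded, and the day-1 grade for every patient in whom the electrode was placed. A patient's own choice to withdraw under section 5.4 is untouched.
- **Later intentional nerve sacrifice or conversion to another dissection:** leave these patients out of the main EMG-weakness analysis, but count them and report them separately by phase, with their log and grade.

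Surgical management is unaffected; section 6.2 already has the surgeon proceed as the patient requires, whatever the study status.

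The cost is a wording amendment and one recorded check before placement. No extra visit is needed, because withdrawn patients are already seen on day 1. However, 6.2 provides only that they are told of the withdrawal then, so grading them must be written in. The downside is that a few less typical patients remain in the analysis set.
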